We will use descriptive statistics to characterize the organizations, providers, and patients, using means and standard deviations, medians and interquartile ranges, or frequencies and percentages where appropriate. Descriptive statistics of central tendency and variability will be generated for outcomes. The distributions of each continuous outcome variable will be assessed for normality, and appropriate transformations will be made if necessary. Two-sample t-tests, Wilcoxon rank-sum tests, and Fisher’s exact test will be used to compare baseline demographic and practice characteristics across intervention arms.

Primary statistical analyses testing the differences in outcome (or change in outcome over time) between intervention groups will be conducted using the intention-to-treat principle. For our clinical outcomes at our primary endpoint of 12 month follow-up, we will select the EMR measure that is closest to 12 months following the baseline survey (enrollment date) for each patient as long as it is within the 6 month window.

General Approach

These analyses will utilize all available data through modeling approaches for correlated outcomes. All missing data will be assumed to be missing at random (MAR) conditioning on the observed data, and models will be adjusted for characteristics associated with missingness and key variables not balanced by the cluster randomization. In sensitivity analyses, missing data will be imputed using likelihood based longitudinal models developed under the MAR assumption. Missing data under plausible informative missing scenarios will be multiple-imputed using these likelihood based models with the mean models tuned according to the plausible informative missing scenarios. These sensitivity analyses will verify the robustness of the results derived under MAR assumption. All tests will be two-sided and significance will be set at $\alpha < 0.05$. Analyses will be conducted using SAS version 9.4 or higher (SAS Institute, Inc., Cary, NC) or Stata SE14 or higher (StataCorp, College Station, TX).

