We will use mixed-effects regression models for continuous outcomes and Generalized Estimating Equations (GEE) analysis for dichotomous outcomes. For mixed-effects regression modeling, we will assume an unstructured correlation structure for longitudinal analyses of outcomes with repeated measurements over time, employ random effects to address clustering by practices, include appropriate covariate adjustment in the fixed effects, and use robust estimates for statistical inferences. The GEE approach is robust to outcome correlation misspecification, so we will just assume an exchangeable correlation structure for the outcomes, include appropriate covariates in the mean model, and use robust estimates for statistical inferences. We will use mixed-effects regression models under the MAR assumption as the basis to conduct multiple imputation for missing BP data or other outcomes as appropriate. In sensitivity analyses evaluating potential impacts under sensible informative missing

(NMAR) scenarios, we will preserve the mixed-effects regression based variance-covariance estimates, and manipulate the mean model under each informative missing scenario to carry out multiple imputation. Missing binary outcomes (e.g., controlled BP or lipids) will be derived based on multiple-imputed continuous values using appropriate observed data likelihood models as described.

Statistical analysis plan for primary outcomes

For the primary clinical outcome of BP control at 12 months we will model the binary variable BP controlled (yes/no) at 12 months using GEE with a logit link on the intervention arm indicator (CC/Stepped Care arm vs. SCP arm). Additional covariates will be included as appropriate as described previously, including appropriate cluster level characteristics and variables associated with occurrence of missing data. With correctly specified mean model, the GEE is robust to misspecification of correlation structure so the statistical inferences will account for outcome correlation due to patients clustering within practice and be valid under MCAR. The regression coefficient for the intervention arm indicator estimates the log-odds ratio of BP control at 12 months for the CC/Stepped Care arm to the SCP arm. Multiple imputation of missing BP outcomes will be carried out to impute the missing BP control outcomes to produce proper inferences under MAR and to conduct sensitive analyses under NMAR scenarios.

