For the primary patient-reported outcome of change from baseline in PAM-13 score at 12 months, we will model the baseline and 12-month PAM-13 measurements using a mixed-effects linear regression model, with the intervention arm indicator (CC/Stepped Care arm vs. SCP arm), 12-month time indicator, and the cross-product term of intervention by time interaction as the fixed mean effects, the practice indicator as a random effect, and additional covariates included as fixed effects as appropriate as described previously. The fixed effect regression coefficient for the cross-product term of intervention by time estimates the mean difference of 12 month change in PAM-13 between arms.

Statistical Analysis Plan for Secondary Outcomes

For the outcomes of systolic and diastolic BP measures at 12 months, we will select the blood pressure measure that is closest to 12 months of follow-up for each patient as long as it is within the 6-month window (either direction). We will model the baseline and 12-month BP measurements using a mixed-effects linear regression model, with the intervention arm indicator (CC/Stepped Care arm vs. SCP arm), 12-month time indicator, and the cross-product term of intervention by time interaction as the fixed mean effects, the practice indicator as a random effect, and adjusting for additional covariates as fixed effects as described previously. The random effect for the cluster ID will be used to capture the outcome correlation for patients nested within the cluster. The fixed effect regression coefficient for the cross-product term of intervention by time estimates the mean difference of 12 month change in BPs between arms.

For the other secondary measures, e.g., laboratory measures of hemoglobin A1c and lipids, we will use methods similar to the assessment of 12 month outcomes for blood pressure, i.e., select the within window measure in the EMR closest to 12 months after baseline and use mixed-effects linear regression or GEE models to assess the outcomes while controlling for outcome clustering within practice.

Subgroup and Exploratory Analyses

Durability of intervention effect at 24 months

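### The PAM-13 and BP change models name no covariate-by-time terms, so covariates entered as main effects leave the arm-by-time estimate unadjusted with complete data and only partly adjusted with missing data

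*Combined protocol and SAP*

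**What the plan says.** Section 8, General Approach, promises that "models will be adjusted for characteristics associated with missingness and key variables not balanced by the cluster randomization". The same section says that the mixed models will "include appropriate covariate adjustment in the fixed effects, and use robust estimates for statistical inferences", and for repeated measurements that "we will assume an unstructured correlation structure for longitudinal analyses of outcomes with repeated measurements over time".

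Under the plan for primary outcomes, the PAM-13 paragraph states that "we will model the baseline and 12-month PAM-13 measurements using a mixed-effects linear regression model", with arm, 12-month time and their product as the mean effects. It then adds "the practice indicator as a random effect, and additional covariates included as fixed effects as appropriate as described previously". The effect to be reported is defined there: "The fixed effect regression coefficient for the cross-product term of intervention by time estimates the mean difference of 12 month change in PAM-13 between arms".

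Under the plan for secondary outcomes, systolic and diastolic BP get the same model, with "the practice indicator as a random effect, and adjusting for additional covariates as fixed effects as described previously". Laboratory values follow similar methods, and the 24-month mixed models again report an arm-by-visit coefficient.

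The plan names its interactions where it wants them: arm by time, arm by 24-month visit, race/ethnicity group by intervention, and clinic by arm. None is covariate by time.

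**The concern.** When the baseline and follow-up values are both responses and the effect is the arm-by-time coefficient, a covariate main effect raises or lowers both visits by the same amount. It describes who scores high or low, not who changes. The difference in change between arms can therefore be distorted by a covariate that is unevenly spread and predicts change, although that covariate is in the model.

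This trial has reason to rely on the adjustment. Only 30 practices were randomized. Section 5 warns that balancing Hispanic patients across arms may be hard because of how practices were allocated. The Missing Data text describes care-manager and community health worker outreach in the intensive arm only, so patient characteristics could relate to missingness differently in the two arms. At stake is whether PAM-13 (primary) and systolic BP (named the most important secondary clinical outcome) are reported as adjusted when the adjustment has not reached the estimate, or has reached it only in part.

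**Working it through.** **Yardstick.** The Power calculation assumes 15 practices of 50 patients per arm, ICC 0.05, two-sided alpha 0.05 and 80% power.
- Design effect: 1 + (50 − 1) × 0.05 = 3.45.
- Effective patients per arm: 750 / 3.45 = 217.4.
- Detectable effect with 28 df: (t₀.₉₇₅ + t₀.₈₀) × √(2/217.4) = (2.048 + 0.855) × 0.0959 = 0.278 SD.
- PAM-13 (SD 10.0): 2.78 points. Systolic BP (SD 19.5): 0.278 × 19.5 = 5.42 mm Hg.

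The plan's figures reproduce.

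**Complete pairs: algebra.** Write the model for patient i in practice j, with time-constant covariate x, as

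Y₀ = b₀ + b₁·arm + g·x + uⱼ + e₀

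Y₁ = b₀ + b₁·arm + b₂ + b₃·arm + g·x + uⱼ + e₁

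1. The change is D = Y₁ − Y₀ = b₂ + b₃·arm + (e₁ − e₀). Both g·x and the practice intercept uⱼ have gone.
2. Take S = Y₀ + cD, with c chosen so that the patient-level residuals of D and S are uncorrelated. S has its own free intercept and arm term (b₀, b₁) as well as g, so it carries no information on b₂ or b₃.
3. Hence the estimate of b₃ is the raw difference in mean D between arms, whatever time-constant covariates are listed.

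**Direct size of an imbalance.** The bias equals the imbalance in x times its effect on change. A 25-percentage-point imbalance and a 5-point effect give 0.25 × 5 = 1.25 points, and 1.25 / 2.78 = 45%. Both inputs are assumed.

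**Incomplete pairs: simulation.** The set-up was 30 practices × 63 patients, practice random intercept, unstructured 2 × 2 patient covariance, generalized least squares, and a true arm-by-time effect of 2.78. Assumptions not in the documents: level effect 3 points per SD of x; effect on change 3 points per SD (0 where marked level only); imbalance 0.5 SD where marked; within-patient correlation 0.5; 60 runs; Monte Carlo SE about 0.06 to 0.08.

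| Scenario | No covariate | Main effect | Main effect + covariate × time |
|---|---|---|---|
| Complete, imbalance | 4.25 | 4.25 | 2.73 |
| 20% missing on x, imbalance | 4.13 | 4.21 | 2.82 |
| 20% missing on x, differing by arm, imbalance | 3.06 | 3.65 | 2.84 |
| 20% missing on x, differing by arm, no imbalance | 1.58 | 2.19 | 2.92 |
| 20% missing on x, differing by arm, no imbalance, level only | 2.42 | 2.86 | 2.86 |

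- Row 1 confirms the identity: the first two columns differ by at most 4 × 10⁻¹⁵. The expected bias is 0.5 × 3 = 1.5; the simulated bias is 4.25 − 2.78 = 1.47.
- In row 3 the no-covariate figure lies closer to 2.78 than the main-effect figure only because two biases offset: imbalance +1.47 (row 1) and missingness 1.58 − 2.78 = −1.20 (row 4).
- In row 5 the main effect does the whole job.
- In row 4 it removes about half of the bias (from −1.20 to −0.59).
- Across the 20%-missing scenarios run, which also included correlations of 0.3 and 0.7, the main effect moved the coefficient by 0.06 to 0.85 points on average.

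**The case against.** **The form is not stated.** The plan nowhere restricts covariates to main effects. In mixed-model language, fixed is the counterpart of random, and a covariate-by-time term would itself be a fixed effect. That stands: main effects only is an inference. It is still the natural reading, because the plan spells out every other interaction it intends.

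**The cancellation needs complete pairs.** The plan expects 20% attrition and uses all available data, so a main effect will move the coefficient. That also stands. A reader might infer that the listed covariates can never alter the effect estimate, or that no adjustment for missingness takes place. The documents do not support either statement. A main effect can fully correct covariate-related missingness when the covariate affects level only. Missingness that depends on baseline PAM-13 or baseline BP is handled by keeping baseline as a response. Multiple imputation and informative-missingness sensitivity analyses are planned as well. The imputation is not a clear rescue, however: it rests on the same class of mixed models, and its covariate form is also unstated.

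**The size is assumed.** The 1.25-point figure is a product of two inputs that are not in the documents. It describes chance imbalance in one realised allocation, not a systematic bias over repeated randomizations. Randomization was stratified by network and blocked, which limits some imbalance. All of this stands. The complete-data identity needs none of these inputs.

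**Conclusion.** The point holds in a bounded form. Read naturally, the PAM-13 and BP change models do not deliver the imbalance adjustment that General Approach promises. With complete pairs the arm-by-time estimate is exactly the unadjusted difference in mean change. With the planned attrition it is adjusted in part: adequately for missingness tied to covariates that affect level only, inadequately for imbalance or missingness involving covariates that predict change.

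The identity rests on two conditions: covariates constant over time, and no time interaction. The size cannot be fixed from the documents. Under the assumptions above, the main-effect bias in the imbalance scenarios with an effect on change ran from 3.65 − 2.78 = 0.87 to 4.25 − 2.78 = 1.47 points. With a level-only covariate and no imbalance it was within simulation error of zero.

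The primary clinical outcome is outside the concern. The 12-month BP-control GEE models a single time point, so covariate main effects do adjust its arm coefficient.

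**What to change.** State the covariate form for every model whose effect is an arm-by-time coefficient: PAM-13, systolic and diastolic BP, laboratory values analysed this way, and the 24-month mixed models. Either of two specifications will do.

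1. Enter each adjustment covariate together with its interaction with time (with each follow-up visit in the 24-month models), and use the same mean structure in the imputation models.
2. Regress the 12-month value on arm, baseline value and covariates, with the practice random effect. Main effects then suffice. Patients without a 12-month value contribute only through the imputation.

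The cost is a sentence or two in the SAP and a few extra model terms. For patient-level covariates this is minor with about 1,500 analysed patients. For practice-level covariates the list should be short, because there are only 30 practices to support those terms.

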For the CC/Stepped Care arm, exploratory analysis will be conducted to determine which parts of the intervention, e.g., number of CM and CHW contacts, were more successful in improving BP control and reducing systolic BP, or if there was an overall “dose” effect.

Power calculation

We aim to recruit a total of $n=1,890$ unique patients. We planned for 20% random attrition which would yield an analytic sample of 1,500 (effective size of 50 patients per practice).^{104,105} A review of cluster-randomized trials in primary care found a median intracluster correlation coefficient (ICC) of 0.04, with an interquartile range of -0.02 to 0.21.¹⁶⁴ Assuming a 5% ICC, 15 clusters of 50 patients per intervention arm and a two-sided alpha of 0.05, we will have 80% power to detect a difference in proportion of patients with BP controlled of 11-13% (depending on whether the proportion controlled in the SCP arm is 50%-70%). With the same assumptions and sample size, using a two-sample t-test, we will be able to detect an effect size of 0.278. Operationalizing this for the primary and important secondary outcomes, we anticipate that for PAM-13, estimating a $SD=10.0$,¹⁶⁵ we would be able to detect a mean difference of 2.78 between the CC/Stepped Care and SCP arms; for systolic BP, estimating a $SD=19.5$ mm Hg,¹⁵³ we could detect a mean difference of 5.42 mm Hg between the CC/Stepped Care and SCP arms.

Design Considerations:

Participants will be considered to be enrolled at the time they are given their randomization assignment, which will occur at the end of the baseline interview. Data from all enrolled participants will be analyzed as intent-to-treat.

Missing Data

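### The PAM-13 and BP change models have no term for practices differing in change, and the plan leaves unstated the robust clustering unit and small-sample correction on which the test then depends

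*Combined protocol and SAP*

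**What the plan says.** All of this is in Section 8 of the combined protocol and SAP.

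- **General Approach.** For repeated measurements, "we will assume an unstructured correlation structure for longitudinal analyses of outcomes with repeated measurements over time". The mixed models will also "employ random effects to address clustering by practices, include appropriate covariate adjustment in the fixed effects, and use robust estimates for statistical inferences". The unit on which the robust variance is clustered is not named, and no correction for the number of practices is given. The Missing Data text mentions robust estimates again, without these details. Mixed-effects models are also the basis for multiple imputation, and missing binary outcomes are derived from imputed continuous values.
- **Primary outcomes, PAM-13.** Baseline and 12-month scores are modelled with arm, time and arm-by-time as fixed effects, "the practice indicator as a random effect, and additional covariates included as fixed effects as appropriate as described previously". The target is stated: "The fixed effect regression coefficient for the cross-product term of intervention by time estimates the mean difference of 12 month change in PAM-13 between arms".
- **Secondary outcomes, systolic and diastolic BP.** The structure is the same, and its practice term is given a purpose: "The random effect for the cluster ID will be used to capture the outcome correlation for patients nested within the cluster".
- **Durability at 24 months.** Change in BP and PAM-13 comes from mixed models over three time points. No practice-by-time term is named there either.
- **Power calculation.** "Assuming a 5% ICC, 15 clusters of 50 patients per intervention arm", with two-sided alpha 0.05 and 80% power, gives a detectable effect size of 0.278.

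**The concern.** The tested quantity is a difference in change. A practice effect that takes the same value at baseline and at 12 months subtracts out of every patient's change, so it cannot represent correlation between the changes of patients in one practice. The unstructured correlation does not help, because it describes repeated measurements within a patient.

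Practices can be expected to differ in change. The intervention starts after baseline, practice teams shape its content and intensity (Section 3F), roll-out is staggered, and Section 8 itself plans an exploratory test of intervention effects that differ across clinics. For systolic BP, entry requires a reading of at least 140 mm Hg and that reading is the baseline. This may narrow practice differences at baseline but not at 12 months.

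At stake are the standard error and type I error for a primary outcome (PAM-13) and for the most important secondary clinical outcome (systolic BP). If the imputation model has the same structure, imputed values would also carry no practice-level variation in change.

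**Working it through.** **Inputs from the plan:** 15 practices per arm, 50 patients each (750 per arm), ICC 0.05, two-sided alpha 0.05, SD 10.0 for PAM-13 and 19.5 mm Hg for systolic BP.

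**Assumptions, not in the documents:** the within-patient correlation r (0.5, varied from 0.3 to 0.7), and the correlation c between a practice's effects at baseline and 12 months (1.0 down to 0). Together with the ICC they fix the ICC of change.

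**1. The plan's own figure.** The design effect is 1 + 49 × 0.05 = 3.45, and the effective n per arm is 750 / 3.45 = 217.4. A noncentral t with 30 − 2 = 28 degrees of freedom gives 0.2784 at 80% power, matching the stated 0.278 (PAM-13 2.78; systolic BP 0.278 × 19.5 = 5.42). A normal approximation gives only 0.269. The stated figure is therefore consistent with both the clustering and 28 degrees of freedom.

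**2. The contrast in the written model.** Let a patient's value be the fixed effects + u (practice) + e1 at baseline or e2 at 12 months. The change is then the time effect + the arm-by-time effect + (e2 − e1), and u is gone. With complete pairs, the model-based variance of the arm-by-time coefficient is Var(change) × 2/750, a design effect of 1.0.

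If practices differ in change with variance T, and patients within a practice with variance S:
- true variance: (2/15) × (T + S/50)
- model-based variance: (2/15) × (T + S)/50
- ratio: 1 + 49 × ICC of change, where ICC of change = T/(T + S)

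**3. Size of a nominal 5% test with the model-based standard error:** 2 × [1 − Φ(1.96/√ratio)].

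| ICC of change | Ratio | Type I error |
|---|---|---|
| 0 | 1.00 | 5.0% |
| 0.01 | 1.49 | 10.8% |
| 0.02 | 1.98 | 16.4% |
| 0.05 | 3.45 | 29.1% |

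With ICC 0.05 at each time and r = 0.5, T = 2 × 0.05 × (1 − c) and S = 2 × 0.95 × 0.5 = 0.95. So c = 0.9 gives 0.01/0.96 = 0.0104, c = 0.8 gives 0.02/0.97 = 0.0206, and c = 0.5 gives 0.05/1.00 = 0.05. At c = 0.8, moving r from 0.3 to 0.7 moves the type I error from 13.6% to 23.0%.

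**4. Simulation.** The written model was fitted by REML with 30 practices of 50, r = 0.5 and no true effect, 2,000 trials per row. Simulation error is about 0.5 to 1 point.

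| c | Model-based | Robust, on patient | Robust, on practice, uncorrected, z | Practice-level, corrected, t(28) |
|---|---|---|---|---|
| 1.0 | 6.0% | 6.1% | 8.1% | 5.8% |
| 0.8 | 16.0% | 16.0% | 7.1% | 5.2% |
| 0.5 | 29.8% | 29.8% | 7.0% | 5.1% |
| 0 | 39.8% | 39.9% | 5.7% | 4.1% |

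The last column uses the standard error that a practice-by-time term would give. The fourth column has an exact value in this balanced normal case. The uncorrected variance is 14/15 of the unbiased one, so the size is the probability that |t(28)| exceeds 1.96 × √(14/15) = 1.894, which is 6.9%.

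**5. Attrition.** With 63 patients per practice at baseline and 50 at 12 months, the cancellation is no longer exact. The model-based size hardly moves: 17.3% at c = 0.8 and 30.1% at c = 0.5.

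**The case against.** The strongest reply is that the plan does not rely on the random intercept alone. The General Approach prescribes robust estimates for every mixed model, and the BP paragraph does not withdraw this. The next sentence of the General Approach uses the same phrase for the GEE. At 12 months the GEE has one BP-control value per patient, so its cluster can only be the practice. In a model with a practice random effect the independent blocks are also practices. Practice is therefore the natural clustering unit, and with it the test is close to valid whatever the random-effects structure. This stands, and it sets the size of the point.

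A reader might infer that the planned PAM-13 test has a type I error of 11-30%. The documents do not support that. Those figures belong to model-based or patient-clustered standard errors, which the plan does not prescribe, and they need a change ICC that the plan does not give. The power section applies 5% to a two-sample t-test and never calls it the ICC of change. At c = 1.0 there is no inflation beyond the nominal level.

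The imputation point can also be contested. The plan states no random-effects structure for the imputation model, and the General Approach places imputation among the sensitivity analyses. However, the primary-outcome text also uses it to obtain inference under MAR for BP control.

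The reply leaves two gaps. The clustering unit decides whether the test is valid, yet it has to be inferred. And even the favourable reading leaves 6.9% rather than 5%, in a design whose 30 practices the protocol itself regards as few.

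**Conclusion.** The point holds as an incomplete specification, not as a demonstrated failure of the planned inference. The model as written has no between-practice variance of change (design effect 1.0), while the power calculation applies 3.45 to PAM-13 and systolic BP. That part is algebra and needs no assumption beyond complete pairs.

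The consequence depends on the standard error:
- **Practice-clustered robust, no correction (natural reading):** about 6-8%.
- **Model-based or patient-clustered:** about 11-30%, assuming a change ICC of 0.01-0.05, and about 5% if practice effects are identical at both times.
- **Practice-level with correction and 28 degrees of freedom:** about 5%.

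The 12-month BP-control GEE is not affected, except through imputed BP values. If the imputation model copies the written structure, robust standard errors cannot put the missing practice-level variation back. The size of that effect has not been quantified. The compression of baseline systolic BP by the entry rule is a reason to expect practices to differ in change, not a measured effect.

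**What to change.** In Section 8:

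1. Add a practice-by-time random effect (practice intercept plus practice-by-visit) to the PAM-13, systolic BP and diastolic BP models, the 24-month mixed models and the imputation model.
2. State that any robust variance is clustered on practice, never on patient.
3. State a small-sample correction with about 28 degrees of freedom (30 practices − 2 arms).

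This takes a few lines of SAP text and no new data. It adds one variance term to estimate. Compared with an uncorrected practice-clustered interval, the corrected one is wider by 2.048 × √(15/14) / 1.96 = 1.08, or about 8%. Under the plan's own assumptions this takes nothing from the stated power, because the 0.278 is already reproduced with a design effect of 3.45 and 28 degrees of freedom.
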